7.5.2. Analysis Methods for Clinical Asthma Exacerbation

As specified in the protocol, because the device-use-measures will be collected continuously over time, these measures could be used to derive many potential predictors of risk. Several analyses are proposed to study correlations between CAE and device-use-measures.

7.5.2.1. Within Patient CAE Analyses

For each CAE event occurring at least 2 weeks after baseline, device-use measures (albuterol use, inhalational flow [MIF], inhalational volume, and time to MIF) will be summarized for each of 2 weeks of interest: first- 'CAE-adjacent week', the week immediately preceding the onset of CAE symptom (ie, day 1 through 7 preceding the date of the CAE symptom onset), and second – 'CAE-Prior Adjacent week', the week preceding that week (ie, during day 8 through 14 preceding the date of the CAE symptom onset). Summary measures of daily and or weekly use will be compared between the two weeks, as proposed below:

Albuterol use measures:

- total number of inhalations in that week
- the maximal daily number of inhalations in that week
- the mean number of daily inhalations (ie, total number of inhalations divided by number of days with number>0)
- occurrence of a single day's albuterol use exceeding 4 inhalations;
- occurrence of a single day's albuterol use exceeding 8 inhalations
- occurrence of a single day's albuterol use exceeding 12 inhalations
- number of days when albuterol use exceeding 4 inhalations;
- number of days when albuterol use exceeding 8 inhalations
- number of days when albuterol use exceeding 12 inhalations

To note, in this analysis, no inhalation in any day will be taken as a 0 count.

Inhalation flow values parameters:

- maximal daily MIF during the week
- minimal daily time to MIF within a week
- maximal total daily inhalational volume within a week,

To note, if no inhalation was taken at a specific day, flow value parameters will be missing and will not be imputed.

Analysis will be based on all patients CAEs for which there are 14 days (or more) prior to the CAE onset, where patient has been on study and CAE free.

Descriptive statistics of use measures in the 'CAE-adjacent week' and 'CAE-Prior Adjacent week' will be presented.

Continuous measures will be compared between the 2 weeks using paired t-test (and Wilcoxon Signed Ranks test) whereas binary patterns will be compared using Mc-Nemar test.

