3. ANALYSIS SETS

3.1. Intent to Treat Analysis Set

The intent-to-treat (ITT) analysis set will include all enrolled patients regardless of whether a patient took any investigational medicinal product (IMP). A patient is considered enrolled according to the status reported in the database. This analysis set will be used for endpoint analysis and safety analysis.

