3.2. Modified Intent-to-Treat Analysis Set

The modified intent-to-treat (mITT) analysis set is a subset of the ITT analysis set that will include patients who used the IMP at any time during the study and patients who did not use the IMP at any time during the study provided these patients complied with study requirements and the data from the ABS eMDPI inhalers were successfully downloaded at the end of the study.

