4.6. Handling Withdrawals and Missing Data

Any data that was collected prior a patient's withdrawal from the study will be used for analysis and presented in the data listings.

The following imputation rules will be used;

- If the return date of the last ABS eMDPI device returned is missing the patient's last date of contact or study completion date will be used as the return date (see Section 4.4 and Section 10.2).
- Adverse events or serious adverse events with missing start dates will be considered treatment emergent (see Section 10.4).
- If a patient never used the ABS eMDPI during the study or download of a given ABS eMDPI device was not successful, study day and weekly inhalational flow values will be missing. If download of a given wrist or ankle accelerometer was not successful, TDS and SDI indices will be missing. These missing data will not be imputed.
- In the derivation of Study Day X Inhalation flow values, if there was no albuterol use on Study Day X , then the closest preceding nonmissing Study Day Inhalation' is used as the 'Study Day X Inhalation' and the inhalational flow values for Study Day X are assigned accordingly (see Section 7.2.1).
- For patients in the ankle accelerometry analysis set if no step data are available for study day 1 through study day 14, the 'baseline TDS' is the first available TDS after study day 14 (see Section 4.2.4).
- For patients in the wrist accelerometry analysis set if no sleep parameter data are available for study day 1 through study day 14, the 'baseline value of a given sleep parameter' is the first available valid sleep parameter value after study day 14 (see Section 4.2.5).

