7. ENDPOINT ANALYSES

All endpoint analyses will be performed using the ITT analysis set.

Data listings will be presented by patient.

7.1. eMDPI: Albuterol Use

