7.1.2. Analysis Methods for Albuterol Use

7.1.2.1. Pattern of Baseline Daily and Weekly Albuterol Use

Summary statistics including 95% CIs of the proportion of eMDPI time on study days when a patient took 0 to 4 inhalations a day (number of days a given patient took 0 to 4 inhalations a day divided by the total number of eMDPI study days for a given patient) will be summarized overall and by CAE status and by CAE severity. In addition, the proportion of patients exhibiting

weekly baseline albuterol use (Week 1, Week 2, ..., Week 12) will be summarized overall and by CAE status and by CAE severity.

Week 1 and Week 2 patient albuterol use patterns, “WK1:I#iD#dMT4Y/N” and “WK2:I#iD#dMT4Y/N” designation, will be summarized descriptively (counts and percent) overall and by CAE status and by CAE severity.

7.1.2.2. Total Number of Inhalations in the Days Preceding the Peak of a CAE

For patients who experienced a CAE, summary descriptive statistics of the total number of inhalations taken in 1 day (eg, the 24-hour period on the day prior to the date of the CAE symptom peak) and at 3, 5, 7, 10, 14, and 21 days preceding the date of the CAE symptom peak will be presented overall and by moderate CAEs and severe CAEs.

In this analysis, among patients experiencing more than 1 CAE, the subsequent CAEs can be considered a separate CAE distinct from the first (preceding) CAE provided the patient exhibited at least 1 day of baseline albuterol use after the first (preceding) CAE’s date of symptom peak and prior to the subsequent CAE’s date of symptom peak. For patients who experience multiple CAEs (eg, 3), for a given number of days preceding a CAE (eg, 21 days), if the (eg, third) CAE overlaps with the time period of the preceding (eg, second) CAE, the CAE (eg, third CAE) should not be included in the analysis.

Mean and 95% CI of the total number of inhalations per day for each eMDPI study day will be summarized graphically. The number of patients contributing to the summary statistic at study at Day 7, 14, 21, 28, 35, 42, 49, 56, 63, 70, 77, and 84 will also be presented. Three line graphs will be presented in 1 figure: “Overall” and by “CAE Status” (Yes, No). Three line graphs will be presented in a second figure; “CAE Status No”, “CAE Status Yes: Severe” and “CAE Status Yes: Moderate”.

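### Inhalation counts have no rule for unread inhalers: unread days stay in the threshold denominators, and the pre-CAE comparison does not require device data

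*SAP*

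**What the plan says.** - **Analysis set.** SAP 7 states: "All endpoint analyses will be performed using the ITT analysis set". SAP 3.1 defines that set as everyone enrolled, with no condition on device data.
- **Failed downloads.** SAP 4.6, repeated in 7.2.1, provides that if "download of a given ABS eMDPI device was not successful, study day and weekly inhalational flow values will be missing". For accelerometers, SAP 4.6 treats step and sleep data in the same way. Neither section mentions inhalation counts.
- **Denominators.** In SAP 7.1.2.1 the number of days with 0 to 4 inhalations is "divided by the total number of eMDPI study days for a given patient". SAP 7.1.2.4 uses the same denominator for days above 4, 12 and 20 inhalations in patients without a CAE. SAP 4.4 runs this time from first dispensing to last return. If the return date is missing, it ends at the earlier of last contact and completion.
- **Pre-CAE comparison.** SAP 7.5.2.1 compares the week before CAE onset with the week before that. Its zero rule is "To note, in this analysis, no inhalation in any day will be taken as a 0 count". Its eligibility rule is "Analysis will be based on all patients CAEs for which there are 14 days (or more) prior to the CAE onset", during which the patient was on study and free of CAE.
- **Devices.** Patients receive inhalers at visit 2 and by courier on Day 21 (SAP 2.1). Usage data are extracted only after the final visit (Protocol 6.1.2).

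**The concern.** The plan foresees that an inhaler may not be read, and it protects the secondary measures. Flow values become missing, and the two accelerometry sets (SAP 3.4 and 3.5) admit only patients whose device was downloaded. The primary predictor has no equivalent protection.

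Two things are at stake. First, the day proportions mix days on which use was observed with days on which it could not be. Second, in the within-patient comparison a week with no data may look like a week with no use. If that happens in only one of the two weeks, the result is a spurious change in albuterol use, which is the signal the study is looking for.

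**Working it through.** **1. The plan's own figures.** 360/(1 − 0.10) = 400 enrolled. 360 × 0.20 = 72 and 360 × 0.25 = 90 events. 360 × 0.067 = 24.1 moderate and 360 × 0.15 = 54 severe, together 78.1. All reproduce and none is disputed. The documents give no figure for unread devices.

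**2. Day proportions.** Let *f* be the share of eMDPI study days that are unread, and assume that use on those days resembles use on read days. Let *p* be the true proportion of days above 4 inhalations and *q* = 1 − *p*. For illustration *p* = 0.30 and *q* = 0.70; neither value comes from the documents.

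- Days above 4: an unread day cannot enter the numerator but stays in the denominator, so the reported value is *p*(1 − *f*).
- Days with 0 to 4, unread days coded 0: *q*(1 − *f*) + *f*.
- Days with 0 to 4, unread days left out of the numerator only: *q*(1 − *f*).

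| Unread *f* | Above 4 (true 30%) | 0 to 4 (true 70%), coded 0 | 0 to 4 (true 70%), left out of numerator |
|---|---|---|---|
| 5% | 28.5% | 71.5% | 66.5% |
| 10% | 27% | 73% | 63% |
| 20% | 24% | 76% | 56% |

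The first result is the same whether unread days are coded 0 or left missing. Its relative size is *f* for any *p*.

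**3. Pre-CAE comparison.** The use level is borrowed from the exacerbating group of the earlier cohort in Protocol 3.3: 5.5 actuations per day, SD 9.7. Per week this is 5.5 × 7 = 38.5, with between-patient SD 9.7 × 7 = 67.9. A simulated paired t-test used 78 events, 4,000 runs, gamma-Poisson weekly totals with an extra week-to-week CV of about 0.32, and a two-sided 0.05 level (assumed, since 7.5.2.1 states none). Here *f* is the share of events affected.

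*Only one week unread and coded 0, no true change.* The expected false difference is *f* × 38.5 inhalations per week. It is negative if the CAE-adjacent week is lost and positive if the prior week is lost.

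| *f* | Size of false difference | Rejection, adjacent week unread | Rejection, prior week unread |
|---|---|---|---|
| 5% | 1.9 | 0.051 | 0.055 |
| 10% | 3.9 | 0.112 | 0.110 |
| 20% | 7.7 | 0.313 | 0.304 |

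With the affected events set to missing, rejection was 0.031 to 0.042. With a true 20% rise (0.20 × 38.5 = 7.7 per week) and 10% of events affected, rejection was 0.100 when the adjacent week was zero-coded, against 0.372 when set to missing. For the prior week it was 0.631 against 0.387.

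*Both weeks unread, true 20% rise.* The mean difference shrinks: 7.43, 6.90 and 6.10 zero-coded, against 7.83, 7.67 and 7.61 set to missing, at 5%, 10% and 20%. Rejection hardly moves: 0.405 against 0.405, 0.384 against 0.385, 0.342 against 0.343. McNemar's test is unaffected because a pair of zeros is concordant, and zero differences drop out of the usual Wilcoxon signed-rank statistic.

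**4. Could the one-week pattern occur?** An inhaler holds 200 actuations (Protocol 5.1.1). At 5.5 per day it lasts 200/5.5 ≈ 36 days. If inhalers are used one after another (an assumption), a 14-day window has 13 internal day boundaries, and 13/36.4 ≈ 0.36 of windows would contain a switch. A switch does harm only if one of the two inhalers was not read.

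**The case against.** The case against is substantial, and most of it stands as a limit on the claim.

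- **A reader might infer that the SAP orders unread days to be scored zero.** It does not. SAP 7.5.2.1 speaks of no inhalation, not of no recorded inhalation, and its companion note on flow values concerns days when none was taken. Protocol 9.3 restricts analysis to observed data. The SAP's precedence clause applies where the documents differ, and silence is not a difference. False zeros are therefore an unclosed risk, not a stated rule.
- **A reader might infer that the move to ITT removed a download safeguard.** The condition in the SAP's mITT definition, "provided these patients complied with study requirements and the data from the ABS eMDPI inhalers were successfully downloaded at the end of the study", applies to patients who never used the product. The protocol's mITT set has no such condition. A user with one unread inhaler meets the same gap in either set.
- **A reader might carry the zero rule into 7.1.2.1 and conclude that the 0-to-4 proportion is inflated.** The rule is confined to its own analysis, so the documents do not fix the direction of that error.
- **A change of device alone does no harm.** A switch between two inhalers that are both read loses nothing.
- **The study is exploratory and no failure rate is given.** This limits what can be said about size.

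None of this repairs the denominators. Leaving unread days missing still keeps them in the eMDPI study days by which the plan divides. Dropping them from both numerator and denominator would be sound, but it is not what 7.1.2.1 and 7.1.2.4 say.

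**Conclusion.** The point holds in two parts of different strength.

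The firm part is the denominator. Followed as written, SAP 7.1.2.1 and 7.1.2.4 divide by days that may have no data. The proportion of days above a threshold is then too low by the unread fraction, whichever way unread counts are handled. At assumed rates of 5%, 10% and 20%, a true 30% becomes 28.5%, 27% or 24%. The 0-to-4 proportion is wrong too, upwards or downwards according to a choice the plan does not make.

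The weaker part is SAP 7.5.2.1. Nothing there requires device data for the 14-day window, so an inhaler unread in one of the two weeks could produce a false change of about 1.9 inhalations per week for each 5% of events affected. A reader might infer that the paired tests are generally unreliable. The working does not support that: when both weeks are unread, mainly the descriptive means shrink.

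The sizes rest on assumed unread rates, on similar use on read and unread days, and, for the paired comparison, on the earlier cohort's use level, a simulation model and wholly unread weeks.

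**What to change.** Amend the SAP as follows.

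- **SAP 4.6:** extend the failed-download rule to inhalation counts. If every inhaler dispensed to a patient was read, all of that patient's study days are covered. Otherwise, a covered day is one within the span of recorded events on the inhalers that were read. Count 0 only on covered days and set other days to missing. Do not set a day to missing merely because some inhaler held by the patient was unread, since one unread spare would then erase fully recorded days.
- **SAP 7.1.2.1 and 7.1.2.4:** use covered days as the denominator.
- **SAP 7.5.2.1:** exclude CAEs whose 14-day window is not covered.
- **Albuterol-count analyses:** leave out patients with no successful download.
- **Reporting:** give the numbers of inhalers dispensed, returned and read.

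This needs SAP wording and a coverage flag built from dispensing, return and download records, with no new data collection. Some patients and events leave the count analyses; how many cannot be foreseen without a failure rate. Coverage of partly read patients is approximate: an unread inhaler may have been used alongside a read one, and a span that begins and ends with a recorded event trims no-use days at its edges.

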2. STUDY OBJECTIVES AND ENDPOINTS

2.1. Study Objectives and Endpoints

The study objectives and endpoints are as follows:

Objective	Endpoints
The objectives of this study are to explore the pattern and amount of albuterol use (as captured in the ABS eMDPI), alone or in combination with other study data, preceding a CAE and in particular, a severe CAE (as diagnosed by the investigators per the protocol). The hypothesis is that albuterol use will increase several days prior to a severe CAE and can serve as a marker of asthma deterioration.	The endpoints of the trial are the primary outcome measure (ie, CAE/severe CAE) and the primary outcome predictor (ie, albuterol use) alone or in combination with secondary predictors (ie, other study data). Multiple correlates of CAE/severe CAE focused on albuterol use, alone or in combination with other study data, will be modeled to determine which patterns best predict the subsequent development of CAE/severe CAE.
	For albuterol use, parameters of interest will include (1) the total number of inhalations in the days preceding the peak of a severe CAE, (2) the number of days prior to the peak of a severe CAE when albuterol use increased, (3) the number of albuterol uses in the 24 hours preceding a severe CAE. Therefore, endpoints are not designated as either primary or secondary. In addition to albuterol use, inspiratory flow values (maximal inhalational flow [MIF], inhalational volume, inhalation duration, and time to MIF), SDI, TDS, and baseline information regarding disease state and demographics will be studied. These data will be analyzed using both a univariate and multivariate approach, to determine which patterns best predict the subsequent development of a moderate CAE or severe CAE. Inspiratory flow values are obtained from the eMDPI, SDI is obtained for a subset of patients who agree to participate at specific sites (n=100) from an accelerometer worn on the wrist, and TDS is obtained for a subset of patients
	who agree to participate at specific sites $(n=100)$ from an accelerometer worn on the ankle. Baseline disease state and demographic information will be obtained at screening.
Another objective for this study is to evaluate the safety of ABS eMDPI use in patients with exacerbation-prone asthma.	 The safety endpoints for this study include the following: adverse event data physical examinations

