9.5.2.1. Endpoint Analysis

The multiple device-use-measures will be used as predictors of CAE in the following stepwise selection logistic regression models to select significant predictors in a forward manner:

- 1. albuterol usage
- 2. albuterol usage + inspiratory flow values
- 3. albuterol usage + SDI

- 4. albuterol usage + TDS
- 5. albuterol usage + inspiratory flow values + SDI
- 6. albuterol usage + inspiratory flow values + TDS

Demographic variables and disease state information collected at study enrollment will also be considered as predictors. Because the device-use-measures will be collected continuously over time, these measures could be used to derive many potential predictors of risk. For example, with respect to albuterol use, a subject using the inhaler 3 times in the span of a 2-day or 3-day period could be a strong predictor of a CAE, but a better marker for risk might be 10 times in the span of a week. There are no prior robust data to inform these decisions; 1 possible benefit of this work will be to examine the relationship between multiple functional forms for the device-use-measures to determine which forms have predictive power.

Furthermore, the effect of including interaction terms in the model (ie, testing the assumption of additivity of predictors on the log odds scale) will also be studied. The primary hypothesis under consideration is that >12 inhalations of SABA dosing will have higher odds of CAE risk relative to 0 to 12 inhalations per day. This dosing scheme is consistent with the approved labelling for albuterol inhalation products. Pair-wise interactions will be assessed at the 0.01 significance level to avoid weak interaction signals that would potentially not translate when applying the risk score to new cohorts. Goodness-of-fit tests may be applied to make sure that the finally selected model fits the data closely. The C-statistic will be used to compare the goodness of fit of various logistic regression models in terms of how well the predictor(s) discriminate between patients with and without CAE (Hosmer et al 2013).

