7.1.2.3. Hypothesis: Albuterol Use Will Increase Several Days Prior to a CAE

The hypothesis under consideration is that albuterol use will increase several days prior to a CAE. Several days will be defined as 7 days prior to the date of the CAE symptom peak for this analysis.

For each subject that experiences at least 1 CAE, Y_1, \dots, Y_7 will represent the number of puffs of albuterol during the 7 days preceding the date of the CAE symptom peak and let Y_8, \dots, Y_{14} will represent the number of puffs taken each day during day 8 through 14 preceding the date of the CAE symptom peak. Under the hypothesis of no increased albuterol use preceding an exacerbation (ie, null hypothesis) assume for subject “xxx” that $Y_i \stackrel{iid}{\sim} Poisson(\lambda_{xxx})$ for all subjects i . Alternatively, if albuterol use does increase prior to an exacerbation, then

$Y_i \stackrel{iid}{\sim} \text{Poisson}(\lambda_{xxx})$ during day 8 through 14 preceding the date of the CAE symptom peak and $Y_i \stackrel{iid}{\sim} \text{Poisson}(\lambda_{xxx} + \delta)$ for the immediate 7 days preceding the CAE(s). Also, for random subject effect, assume λ_{xxx} follows some distribution to account for subject to subject variability. Let d_{xxx} will equal to the mean number of puffs during the 7 days immediately preceding the date of the CAE symptom peak minus mean number of puffs during days 8 through 14 preceding the date of the CAE symptom peak. To assess if albuterol usage increases 7 days prior to a CAE, $H_0: \mu_D = 0$, $H_1: \mu_D > 0$ will be tested using a t-test at the 0.05 significance level.

7.1.2.4. Number of Days Prior to the Peak of a CAE When Albuterol Use Increased

Among patients who experienced a CAE, summary statistics of the number of days prior to the peak of a CAE when albuterol use increased will be presented overall and by moderate CAEs and severe CAEs for 3 thresholds defining an increase in albuterol use;

- (i) First occurrence of a single day's albuterol use exceeding 4 inhalations;
- (ii) First occurrence of a single day's albuterol use exceeding 12 inhalations;
- (iii) First occurrence of a single day's albuterol use exceeding 20 inhalations.

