Among patients who did not experience a CAE, summary statistics, including 95% CIs, of the proportion of eMDPI time on study days when a patient exceeded a given threshold of albuterol use (number of days a given patient's single day's albuterol use exceeded 4 inhalations / total number of eMDPI study days for a given patient) will be summarized for 3 thresholds defining an increase in albuterol use;

- (i) a single day's albuterol use exceeding 4 inhalations;
- (ii) a single day's albuterol use exceeding 12 inhalations;
- (iii) a single day's albuterol use exceeding 20 inhalations.

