7.5.2.2. Time to Clinical Asthma Exacerbations Short-term Exacerbation Risk (7 days)

For each patient, the following 3 landmark use events will be identified:

- first time in study when had >4 inhalations per day ("low use group")
- first time in study when had >8 inhalations per day ("medium use group")
- first time in study when had >12 inhalations per day ("high use group").

A patient may be included in more than 1 landmark use group (for example, if had >12 inhalations a day any time during study, then on that time or already before he/she also had >8 and >4 a day).

For each landmark use groups, time to CAE within 7 days since the landmark event will be estimated and plotted using Kaplan-Meier plot. The 3 groups will be presented in the same plot, to assess a possible 'dose-response' association, if higher use is associated with shorter time to CAE.

If a CAE has not occurred within 7 days, then that observation will be censored at 7 days or earlier if follow-up had completed/terminated before 7 days elapsed. Note, if CAE occurred on the same date where landmark use happened, then time to CAE will be calculated as 0.

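### The named significance tests of albuterol use before a CAE compare two weeks inside CAE cases only, and no planned analysis tests that change against CAE-free windows

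*SAP*

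**What the plan says.** SAP 1.1 and Protocol 2.1 hypothesise that albuterol use goes up some days ahead of a severe CAE and can act as a marker of deterioration. They also aim to find the patterns that best predict a CAE.

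Two sets of significance tests address use before a CAE:

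- **SAP 7.1.2.3.** "For each subject that experiences at least 1 CAE", mean daily puffs on days 8 to 14 before the symptom peak are subtracted from the mean on days 1 to 7. The alternative is a positive mean difference, so the test is one-sided; it "will be tested using a t-test at the 0.05 significance level".
- **SAP 7.5.2.1.** The same two weeks are used, counted back from symptom onset. "Analysis will be based on all patients CAEs for which there are 14 days (or more) prior to the CAE onset", with the patient on study and CAE-free. "Continuous measures will be compared between the 2 weeks using paired t-test (and Wilcoxon Signed Ranks test) whereas binary patterns will be compared using Mc-Nemar" tests. No level or sidedness is given.

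Other analyses include patients or days without a CAE:

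- **7.1.2.1, 7.1.2.2 and 7.1.2.5** summarise use by CAE status: proportion of days at 0 to 4 inhalations, mean inhalations per study day, and maximum in 24 hours.
- **7.1.2.4** gives days from first threshold exceedance to peak for CAE patients. The others get a different statistic: "Among patients who did not experience a CAE, summary statistics, including 95% CIs, of the proportion of eMDPI time on study days" above each threshold.
- **7.5.2.2** starts a Kaplan-Meier curve at each patient's first day above 4, 8 or 12 inhalations. "If a CAE has not occurred within 7 days, then that observation will be censored at 7 days or earlier".
- **7.5.2.3** offers, as one possibility, a next-day prediction model on all CAE-free days.
- **Protocol 9.5.2.1** plans logistic models judged on "how well the predictor(s) discriminate between patients with and without CAE". SAP 7.5.3 and 20.4 move these to a separate report.

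**The concern.** A marker needs two frequencies: how often the rise comes before a CAE, and how often the same rise occurs with no CAE after it. The two sets of tests bear only on the first. Using the patient's own prior week as control removes fixed patient traits. It does not remove a trend over study time, because the CAE-adjacent week is always the later one. Nor does it account for rises that settle without a CAE. Drift could create an apparent signal or hide a real one.

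These are the only named tests of the study's central hypothesis, so a small p-value from them is likely to be read as support for the marker claim. It would support only the statement that use was higher in the later week among people who went on to a CAE.

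**Working it through.** **1. The plan's own figures (SAP 2.3).** Evaluable patients: 400 × 0.90 = 360. CAEs: 360 × 0.20 = 72 to 360 × 0.25 = 90. By severity: 360 × 0.067 = 24 moderate and 360 × 0.15 = 54 severe, total 78. All reproduce. The documents give no power, effect size or SD for either set of tests.

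**2. Who enters the tests.** Assuming one CAE per patient, 360 − 90 = 270 to 360 − 72 = 288 evaluable patients (75% to 80%) are outside both. If CAEs fall evenly over 84 days (assumed), 70/84 of them meet the 14-day rule in 7.5.2.1: 72 × 70/84 = 60 to 90 × 70/84 = 75.

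**3. Case-only test when the rise carries no information.** Suppose the mean week-to-week change is d SDs both before CAEs and in ordinary fortnights. The chance that a one-sided t-test at 0.05 rejects comes from the noncentral t distribution with n − 1 df and noncentrality d√n:

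| n cases | d = 0.1 | d = 0.2 | d = 0.3 | d = 0.4 | d = 0.5 |
|---|---|---|---|---|---|
| 60 | 19.0% | 45.5% | 74.3% | 92.2% | 98.5% |
| 72 | 21.1% | 51.4% | 81.0% | 95.7% | 99.5% |
| 75 | 21.6% | 52.8% | 82.4% | 96.3% | 99.6% |
| 90 | 24.1% | 59.4% | 88.1% | 98.3% | 99.9% |

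Rows 72 and 90 suit 7.1.2.3; rows 60 and 75 suit 7.5.2.1. If 7.5.2.1 is two-sided at 0.05, the d = 0.3 figures are 62.8% (n = 60) and 72.7% (n = 75).

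**4. Same data, with comparators.** In 20,000 simulated trials with d = 0.3 in both groups, comparing the cases' change with one window from each of 270 to 288 patients without a CAE rejected in 4.8% to 5.0%. For a true excess of 0.3 SD, power is 68% to 79% one-sided, or 56% to 69% two-sided. For 0.4 SD it is 88% to 95%, or 80.5% to 90.8%. The comparison is feasible at the planned size.

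**5. Why the missing frequency matters.** Base rate per patient-week: 78/(360 × 12) = 78/4,320 = 1.81%. Suppose a rise precedes 60% of CAEs (assumed) and occurs in a proportion f of CAE-free windows. Then predictive value = 0.6 × 0.0181 / (0.6 × 0.0181 + f × 0.9819).

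| f (assumed) | Predictive value |
|---|---|
| 0.05 | 18% |
| 0.15 | 7% |
| 0.30 | 3.5% |

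Neither set of tests estimates f.

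**6. Do the other analyses supply the comparison?** The landmark curves in 7.5.2.2 cover first crossings of fixed thresholds, not a rise. Their groups are nested, no test is named, and there is no group at or below 4 inhalations a day. The two halves of 7.1.2.4 are on different scales. The plots in 7.1.2.2 by CAE status run along study day and are not aligned to events. The model in 7.5.2.3 is optional, and 7.5.3 gives no detail.

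**The case against.** The strongest defence is that the paired tests answer their own question. The hypothesis that use climbs before a CAE is a within-patient statement, and SAP 7.5.2 says several analyses are proposed. The study is exploratory, assesses no efficacy and designates no primary endpoint. All of this stands, and it bears on how serious the gap is. It does not cover the second half of the hypothesis, that use can act as a marker.

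Three stronger readings are tempting, and the documents support none of them.

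- A reader might infer that the trial cannot support any prediction claim. Use is recorded in every patient. SAP 7.5.2.2 and 7.5.2.3 bring in CAE-free patients or days, and the logistic models are deferred, not dropped.
- A reader might infer that false alarms and predictive value will be wholly unknown. One minus the landmark curve at day 7 estimates the CAE risk after a first threshold crossing, which is a partial predictive value.
- A reader might infer that the logistic models must rely on quantities such as "the total number of inhalations in the days preceding the peak of a severe CAE", which patients without a CAE do not have. Protocol 9.5.1 lists these as examples. Protocol 9.5.2.1 speaks of albuterol usage in several functional forms, with weekly and multi-day counts that exist for everyone.

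Drift would also be partly visible in the daily plots by CAE status, and the documents give no evidence that it occurs. But seeing a trend on a plot does not adjust the test for it.

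**Conclusion.** The point holds in a limited form. The SAP pre-specifies no comparison of the pre-CAE week-to-week change with the same change in CAE-free windows. A significant result in 7.1.2.3 or 7.5.2.1 therefore shows a later-week increase among cases and nothing about specificity. Under an assumed uninformative rise of 0.1 to 0.5 SD, the one-sided case-only test rejects in 19% (60 cases, 0.1 SD) to 99.9% (90 cases, 0.5 SD) of trials.

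These figures rest on an assumed effect size, normal changes, one CAE per patient and even timing of CAEs. The predictive values also rest on assumed frequencies. They show how much depends on the missing quantity and do not forecast this trial's result. Because the study is exploratory and other analyses cover part of the ground, the point is worth acting on but should not block the analysis.

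**What to change.** Keep the planned tests and label them as descriptive within-case results. In SAP 7.5.2.1 and 7.1.2.3, add:

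1. **Comparator fortnights.** For each analysed CAE, take index days on the same study day from any patient who has been on study and CAE-free for the preceding 14 days and stays CAE-free for the next 7. Include CAE patients during their CAE-free time. Cases must meet a matching eligibility rule; 7.1.2.3 currently states none, so one is needed there.
2. **Estimate.** Report the CAE-minus-comparator difference in week-to-week change with a patient-clustered 95% CI.
3. **Marker performance.** For each threshold, report sensitivity and false-alarm proportion.
4. **Predictive value.** Compute it from all eligible patient-days or with sampling weights. If, say, four comparators per CAE were sampled and left unweighted, the base rate would be 1/5 = 20%. With the 60% and 15% used above, predictive value would then come out as 0.6 × 0.2 / (0.6 × 0.2 + 0.15 × 0.8) = 0.12/0.24 = 50%, instead of 7%.

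The cost is SAP wording, programming on data already recorded, one more table and a stated index-day rule (with a fixed seed if windows are sampled). SAP 2.4.2 requires amendments to be approved before database lock, so the rule should be set by then.
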